5.2. Treatment Assignment

Subjects will be assigned to study treatment in accordance with the randomization schedule generated prior to the start of the study by the study statistician, using the validated internal software RANDALL.

Each subject scheduled to receive study medication will receive a treatment allocation number when randomized. The randomization number will indicate which therapy the subject will receive, the treatment allocation ratio will be 2:1 (TQ/CQ: PQ/CQ). Once a randomization number has been allocated to a subject, it cannot be re-assigned to any other subject.

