8.2. Study Design Considerations

8.2.1. Sample Size Assumptions

The sample size of 300 is based on the regulatory requirement to obtain an appropriate total safety database in subjects treated with TQ/CQ at the selected dose, given that subjects are randomized to TQ/CQ: PQ/CQ on a 2:1 ratio.

Included in this sample is a key subgroup of a minimum of 50 female subjects with moderate (40-70%) G6PD enzyme activity. This subgroup will be used to assess the risk to G6PD heterozygous deficient females who may be misclassified by a G6PD POCT and inadvertently treated with TQ.

[figure not shown]
The proportion of heterozygous subjects in this subgroup who will meet the primary endpoint of clinically relevant hemolysis when treated with either TQ or PQ is assumed to be 50%. A sample size of 30 such subjects treated with TQ will provide precision of 18% for the 95% confidence interval. Similarly, sample size of 15 subjects treated with PQ will provide a precision of 25%.

With 50% of the subjects in the subgroup and none of the other subjects assumed to meet the primary endpoint, we expect 8% of the total cohort to have a clinically relevant hemolysis. The 200 subjects in the TQ group will provide a precision of 4% and the 100 subjects in the PQ group precision of 5% for the 95% CI.

The power for testing a difference in proportion between the two treatment groups will be provided retrospectively.

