7.1.2. Planned Safety Statistical Analyses

Primary Statistical Analyses
Endpoint(s)

 Occurrence of clinically relevant haemolysis in all subjects. See Section 13.6.3 for derivation of clinically relevant haemolysis.
Model Specification

 No formal statistical analyses will be performed as the incidence of clinically relevant haemolysis is expected to be low. 95% confidence intervals for the proportion of subjects (\hat{p}) with clinically relevant haemolysis in each treatment group (i, j) will be based in the Wilson score: $\left(\hat{p}_i + z_{\alpha/2}^2 / 2n_i \pm z_{\alpha/2} \sqrt{(\hat{p}_i(1 - \hat{p}_i) + z_{\alpha/2}^2 / 4n_i) / n_i} \right) / 1 + z_{\alpha/2}^2 / n_i$ This can be obtained in SAS using the BINOMIAL option in PROC FREQ. The Newcombe method based on the Wilson score will be used to calculate the 95% confidence interval for the difference in proportion ($\hat{p}_i - \hat{p}_j$) (Newcombe, 1998): $\text{lower limit} = (\hat{p}_i - \hat{p}_j) - \sqrt{(\hat{p}_i - L_i)^2 + (U_j - \hat{p}_j)^2}$ $\text{upper limit} = (\hat{p}_i - \hat{p}_j) + \sqrt{(U_i - \hat{p}_i)^2 + (\hat{p}_j - L_j)^2}$ where U and L represent the upper and lower limit respectively of the corresponding

Primary Statistical Analyses

proportion. This can be obtained in SAS using the RISKDIFF option with (CL=(NEWCOMBE)) in PROC FREQ.

Results Presentation

 Table 3.1, Figure 3.1: The proportion of subjects with clinically relevant haemolysis in each treatment group will be presented together with a confidence interval based on the Wilson score The difference between treatment groups in the proportion of subjects with clinically relevant haemolysis in each treatment group will be presented together with a confidence interval based on the Newcombe method (tables only) Due to the low number of G6PD deficient females expected, they will be included in the primary analysis but their data will be listed separately.

Sensitivity and Supportive Statistical Analyses

 To assess the impact of missing data, a sensitivity analysis will be performed using imputed data where data is missing, as described in Section 13.7.2.3 and the methodology detailed above (Table 3.2).

Further safety analyses are described in Section 8.2.

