3. DATA SOURCES/STUDIES INCLUDED

- The individual patient data from the PQ+CQ and CQ only arms of the DETECTIVE Part 1 study will be used alongside published data and clinical opinion to define the non-inferiority limit (further details in Section 9.2)
- The individual patient data from the TQ+CQ and PQ+CQ arms of the DETECTIVE Part 2 and GATHER studies will be used to calculate a combined hazard ratio and 95% confidence interval (further details in Section 9.4).

DETECTIVE Part 1

TAF112582 (DETECTIVE) is a seamless phase II/III, multi-centre, double-blind, double-dummy, parallel group, randomised, active control study. In Part 1 (phase 2b) of the study, all subjects were treated with CQ on Days 1 to 3 (600 mg, 600 mg, 300 mg) to treat the blood stage malaria infection. Subjects were randomised to one of six groups (ratio 1:1:1:1:1:1):

- Placebo (CQ only),
- Single dose TQ 50mg,
- Single dose TQ 100mg,
- Single dose TQ 300mg,
- Single dose TQ 600mg, or
- 15mg PQ od for 14 days.

A total of 329 subjects were enrolled in this study. Subjects were followed up for six months to assess the proportion of subjects who remained relapse free in that time.

DETECTIVE Part 2

The Part 2 of TAF112582 is a Phase III confirmatory trial which is currently ongoing and has enrolled 522 subjects. All subjects received open label CQ for the first three days of the study to treat the blood stage of the infection. Subjects were randomised to one of three groups (ratio 2:1:1):

- Single dose TQ 300mg,
- PQ 15 mg od for 14 days, or
- Placebo (CQ only).

The primary endpoint (% relapse-free efficacy over six months) is the same as for Part 1 (phase 2b) of the study.

GATHER

The phase III study TAF116564 (GATHER) is similar in design to pivotal Part 2 of DETECTIVE. It is a prospective, double-blind, multicenter study where a total of 251 subjects have been randomised. All subjects received open label CQ for the first three days of the study to treat the blood stage of the infection. Subjects were randomised to one of two groups (ratio 2:1):

- Single dose TQ 300mg, or
- PQ 15mg od for 14 days.

This study does not contain a placebo arm, as the primary endpoint is safety, and efficacy is a secondary endpoint. However, efficacy assessment methodology and timings, and duration of follow-up are identical to DETECTIVE.

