8.4. Subgroup and Covariate Definitions

Both study and region will be included as covariates. The randomisation was not stratified for both DETECTIVE Part 2 and GATHER, so no additional covariate adjustment is required.

Breakdown of countries within each study

Countries	DETECTIVE Part 2	GATHER
Brazil	x	x
Peru	x	x
Thailand	x	x
Philippines	x	
Ethiopia	x	
Cambodia	x	
Colombia		x
Vietnam		x

Regions are defined geographically for inclusion as a covariate as:

Region	Countries
South America	Brazil, Peru, Colombia
Asia	Thailand, Vietnam, Cambodia, Philippines
Africa	Ethiopia

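### The primary haemolysis difference ignores screening G6PD class, so the chance split of deficient women between arms widens its interval; a G6PD-stratified difference in the RAP would recover that precision cheaply

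*Supplement*

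**What the plan says.** Protocol Amendment 5, section 5.2, describes a computer-generated schedule at 2:1 and names no stratification factor: "The randomization number will indicate which therapy the subject will receive, the treatment allocation ratio will be 2:1 (TQ/CQ: PQ/CQ"). RAP 2.3 adds only that allocation is central, through an interactive voice system. Meta-Analysis Plan 8.4 is explicit: "The randomisation was not stratified for both DETECTIVE Part 2 and GATHER, so no additional covariate adjustment is required". GATHER is this trial (Meta-Analysis Plan, section 3: "The phase III study TAF116564 (GATHER) is similar in design to pivotal Part 2 of DETECTIVE").

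G6PD activity as a percentage of the site median is measured at screening to decide eligibility (Protocol 3.2 and 4.2.1), so the class is known before allocation. Protocol 8.2.1 makes it the decisive predictor: "Included in this sample is a key subgroup of a minimum of 50 female subjects with moderate (40-70%) G6PD enzyme activity"; the proportion of heterozygous women in it "who will meet the primary endpoint of clinically relevant hemolysis when treated with either TQ or PQ is assumed to be 50" per cent; and the overall rate is derived "With 50% of the subjects in the subgroup and none of the other subjects assumed to meet the primary endpoint".

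RAP 2.1 later drops estimation in that subgroup because recruitment was difficult, and leaves the all-subject treatment difference as the only primary objective. RAP 7.1.2 keeps the deficient women in that analysis and specifies: "The Newcombe method based on the Wilson score will be used to calculate the 95% confidence interval for the difference in proportion". The interval is unadjusted. RAP 13.10.1 names only region and chloroquine supply date as covariates, and both serve the efficacy models.

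**The concern.** If one baseline class carries most of the risk, the arm that draws more of its members will show more haemolysis even when the two drugs are identical. Neither the allocation nor the analysis controls this. The trial tests no hypothesis (RAP 2.4), so the estimate and its interval are its whole primary result. Extra width from a factor already measured at screening is avoidable, and a difference between arms cannot be told apart from an uneven split of deficient women without reading the separate listing.

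**Working it through.** **Inputs.** Planning case, Protocol 8.2.1: 200 TQ, 100 PQ, 50 deficient women, risk 50% in that class and 0% elsewhere. Number randomised, Meta-Analysis Plan section 3: 251, taken as 167 and 84. The documents give no final count of deficient women; 5 to 20 is an assumption. Background risk of 1 to 4% in other subjects is also an assumption.

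**The plan's own figures.** Half-width = 1.96·√(p(1−p)/n).
- p = 0.5: 17.9% (n = 30) and 25.3% (n = 15); stated 18% and 25%.
- p = 0.08: 3.8% (n = 200) and 5.3% (n = 100); stated 4% and 5%.
- Overall rate: 25/300 = 8.3%, or 22.5/300 = 7.5% if 45 of the 50 are heterozygous; stated 8%.

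All reproduce.

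**Variance of the TQ−PQ difference.** Let c = 1/nT + 1/nC, let K be the number of deficient subjects among N, let q and q0 be the risks in deficient and other subjects, and let X be the number of deficient women on TQ.
- Within classes: [(K/N)q(1−q) + (1−K/N)q0(1−q0)]·c
- From the chance split: [(q−q0)c]²·Var(X), where Var(X) = K(nT/N)(nC/N)(N−K)/(N−1)

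A difference stratified by class removes the second part.

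**Planning case.** c = 0.015.
- Within: (50/300)(0.25)(0.015) = 0.000625, SE 2.50 points.
- Var(X) = 50(2/3)(1/3)(250/299) = 9.29, SD 3.05; 95% range 27 to 39 deficient women on TQ.
- Chance split: (0.5 × 0.015)² × 9.29 = 0.000523, SD 2.29 points.
- Total: 0.001148, SE 3.39 points.

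The half-width is 6.6 points crude and 4.9 stratified, which is 26% narrower. The split supplies 0.000523/0.001148 = 45.5% of the variance.

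**251 randomised, 50% risk in deficient women.** Entries are the crude and stratified 95% half-widths in points, with the reduction.

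| Deficient women | Others 0% | Others 1% | Others 2% | Others 4% |
|---|---|---|---|---|
| 5 | 2.61 → 1.85 (29%) | 3.65 → 3.18 (13%) | 4.44 → 4.08 (8%) | 5.67 → 5.41 (5%) |
| 10 | 3.67 → 2.62 (29%) | 4.44 → 3.66 (18%) | 5.09 → 4.45 (13%) | 6.15 → 5.67 (8%) |
| 20 | 5.13 → 3.70 (28%) | 5.67 → 4.47 (21%) | 6.14 → 5.11 (17%) | 6.98 → 6.16 (12%) |

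Simulating a plain Mantel-Haenszel difference after unstratified allocation gives 29 to 36% at 0% background risk and 5 to 22% at 1 to 4% (about 0.3 to 1.5 points). The 36%, at five women, overstates the gain: the deficient stratum gets zero weight whenever one arm has none. With a fallback to the crude difference in that event, the gain at five women is about 22% at 0% background risk.

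**Bias, coverage and the role of the schedule** (400,000 simulated trials, planning case):
- Unstratified allocation, crude Newcombe: mean error 0.00, coverage 95.3%, mean width 13.8 points.
- Stratified allocation, same Newcombe interval: width still 13.8 points, coverage 99.2%.
- Unstratified allocation, estimate post-stratified by class: SE 2.54 points, against 2.50 with stratified allocation.

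The gain comes from the estimator, not from the schedule.

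**Empty stratum.** With 5 deficient women split 167:84, the chance that one arm has none is 0.128 + 0.004 = 13%. With 10 it is about 1.5%.

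**The case against.** The strongest reply is that nothing here is wrong, only less efficient than it might be. No test is planned, the estimate is unbiased, and the Newcombe interval already carries the variance of the split. That stands. A reader might infer bias or an invalid interval, and the simulation shows neither.

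A reader might also blame the unstratified schedule. Stratified allocation with the planned interval would leave the reported width unchanged, and once the analysis is stratified it adds almost nothing. The operative choice is in RAP 7.1.2, not Protocol 5.2.

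The 50% against 0% contrast is a sample-size simplification. Protocol 3.3.1 reports that 4% of phase II subjects on 300 mg fell by more than 2.5 g/dL, judged disease-related, so some events outside the deficient class are plausible. RAP 7.1.2 expects few deficient women and a low incidence. Both shrink the absolute gain, at the low end to about 0.3 point.

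A further tempting inference is that the 30 TQ and 15 PQ women behind the 18% and 25% precisions are not secured; among 50 women the chance of missing at least one count is about 35%. That no longer bears on a planned result, since RAP 2.1 does not estimate the subgroup, and Protocol 8.2.2 already allows for 18 or 24 on TQ.

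The best practical objection is sparsity: a plain Mantel-Haenszel estimate would give the deficient stratum zero weight if one arm had none, removing the women of most safety interest. The fix has to prevent this.

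**Conclusion.** The point holds as a cheap gain in precision for the trial's only primary estimate, not as a fault in validity. The planning-case size, SE 3.4 against 2.5 points, rests on 50 deficient women and should not be read as the loss in the trial as recruited. For 251 randomised, the realistic range is about 0.3 to 1.4 points of half-width by the formula. It depends on two quantities the documents do not give: the number of deficient women and the risk in other subjects. A smaller contrast also reduces it: with 20% rather than 50% risk in the deficient class, the crude SE exceeds the stratified one by only 10 to 12%. Coverage of a stratified interval with very few women in one stratum was not checked, which is another reason to keep the crude interval in view.

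**What to change.** In RAP 7.1.2, before unblinding:
- Give the TQ−PQ difference in haemolysis stratified by screening G6PD class (≥40 to <70% against ≥70% of site median), as a Mantel-Haenszel risk difference or a stratified Newcombe interval, alongside the crude Newcombe difference.
- State that the crude difference stands as primary if the deficient stratum is empty in one arm, so that those women never leave the primary estimate.
- Report the number of deficient women by arm beside both estimates.

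The cost is a few sentences and one more row in Table 3.1; no new data are needed. The downside is a sparse stratum when few deficient women enrol. The fallback has a small price of its own: with five women at 50% risk and identical drugs, it shifts the expected difference by about 0.128 × (2.5/167) − 0.004 × (2.5/84) = 0.18 point, and by about 0.05 point with ten. Stratifying the allocation schedule by the same class is optional and would matter only to a future trial; with 251 already randomised, the analysis change recovers nearly all of the gain.

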5.3. Blinding

This is a double-blind study and both subject and study staff will remain blinded to treatment.

The investigator or treating physician may unblind a subject's treatment assignment **only in the case of an emergency or in the event of a serious medical condition**, when knowledge of the study treatment is essential for the appropriate clinical management or welfare of the subject, as judged by the investigator. Investigators have direct access to the subject's individual study treatment. It is preferred (but not required) that the investigator first contacts the GSK Medical Monitor or appropriate GSK study personnel to discuss options **before** unblinding the subject's treatment assignment. If GSK study personnel are not contacted before the unblinding, the investigator must notify GSK as soon as possible, but without revealing the treatment assignment of the unblinded subject, unless that information is important for the safety of subjects currently in the study. The date and reason for the unblinding must be fully documented in the appropriate data collection tool.

GSK's Global Clinical Safety and Pharmacovigilance (GCSP) staff may unblind the treatment assignment for any subject with an SAE. If the SAE requires that an expedited regulatory report be sent to one or more regulatory agencies, a copy of the report, identifying the subject's treatment assignment, may be sent to clinical investigators in accordance with local regulations and/or GSK policy.

5.4. Product Accountability

In accordance with local regulatory requirements, the investigator, designated site staff, or head of the medical institution (where applicable) must document the amount of investigational product dispensed and/or administered to study subjects, the amount returned by study subjects, and the amount received from and returned to GSK, when applicable. Product accountability records must be maintained throughout the course of the study.

5.5. Treatment Compliance

Compliance with study medication will be assessed in all subjects by directly observing the taking of medication for days 1-3 of the study. Compliance with respect to PQ medication/placebo in the subgroup of female subjects with moderate G6PD deficiency will be assessed for days 4-15 also by directly observing the taking of study medication. In all other subjects, outpatient compliance will be assessed by pill count and will be evaluated using details of dose administration recorded in the eCRF.

As part of the assessment of PQ compliance, levels of PQ and 7-carboxy PQ will be measured on Days 2, 3, 8 and 15 using TQ pharmacokinetic samples (see Section 6 and Section 6.6.1). Refer to the SPM for detailed methodology on measuring PQ and 7-carboxy PQ in these samples.

5.6. Concomitant Medications and Non-Drug Therapies

5.6.1. Permitted Medications and Non-Drug Therapies

5.6.1.1. Concomitant Medication

All subjects can be given paracetamol during the study but administration time must be recorded in the eCRF. Allowable antibiotics are penicillins, cephalosporins, carbapenems and aminoglycosides.

All concomitant medications (prescription and non-prescription) taken during the study should be recorded in the eCRF. The minimum requirement is drug name and date of administration.

5.6.1.2. Rescue Medication

Subjects requiring rescue medication will be given appropriate medication in accordance with site (local) or national treatment guidelines for *P. vivax* malaria or; e.g., *P. falciparum* malaria, whichever is applicable. Subjects offered rescue medication should be followed up for safety assessment until resolution of the malaria infection.

Details of rescue medication including reason for the rescue medication offered (e.g. withdrawal from study, treatment failure) should be recorded in the eCRF.

5.6.2. Prohibited Medications and Non-Drug Therapies

The following drugs are prohibited for use from 30 days prior to entry in the study through Day 180:

- Anti-malarials and other medicines with known anti-malarial activity.
- Drugs with hemolytic potential.
- Drugs known to prolong QTcF
- Drugs known to interact with primaquine or chloroquine.

The use of herbal remedies during the course of the study is to be avoided. However, if taken this should be recorded in the eCRF under concomitant medication.

See [Appendix 5](#) in Section 11.5 for a non-exhaustive list of prohibited medicines for guidance.

5.7. Treatment after the End of the Study

There is no extension study planned and thus no post study treatment will be offered except for subjects diagnosed with malaria at the end of the study who will receive rescue medication outlined in Section 5.6.1.2.

The investigator is responsible for ensuring that consideration has been given to the post-study care of the patient's medical condition whether or not GSK is providing specific post study treatment.

5.8. Treatment of Study Treatment Overdose

An overdose for this study will be considered as any dose of study medication that is more than the planned dose on each dosing occasion.

Tafenoquine

No specific antidote for tafenoquine has been identified. In the event that overdose or toxicity occurs, individuals should be managed with appropriate supportive measures and clinical judgement. Immediate induction of emesis and/or gastric lavage is not recommended. Hemodialysis is unlikely to be clinically useful as tafenoquine is highly protein-bound.

Methemoglobinemia has been observed in clinical trials at therapeutic doses of tafenoquine; clinically significant levels could possibly be encountered in overdose.

Chloroquine

No specific antidote for chloroquine has been identified. In the event that overdose or toxicity occurs, individuals should be managed with appropriate supportive measures and clinical judgement. Immediate induction of emesis and/or gastric lavage is not recommended.

Drowsiness, blurred vision, diplopia, blindness, tinnitus, convulsions and coma can occur with overdose. Chloroquine is a known cardiovascular toxin thus cardiac monitoring and resuscitation facilities are essential. Thus in addition to dizziness, nausea, vomiting, diarrhea and headache hypotension, cardiogenic shock and cardiac arrest may occur. The 12 lead ECG may demonstrate decreased T waves, widening of the QRS complex, which may lead to ventricular tachycardia and/or fibrillation.

Primaquine

No specific antidote for primaquine has been identified. In the event that overdose or toxicity occurs, individuals should stop the medication and be managed with appropriate supportive measures and clinical judgement. Immediate induction of emesis and/or gastric lavage is not recommended.

Symptoms of primaquine overdose include abdominal cramps, vomiting, burning epigastric pain, central nervous system and cardiovascular disturbances, cyanosis, methemoglobinemia (see tafenoquine overdose guidelines), moderate leukocytosis or leukopenia and anemia.

6. STUDY ASSESSMENTS AND PROCEDURES

Table 2 Time and Events

Protocol Activity	Visit Day															
	Screening/Treatment Period ^a							Follow-Up Period							Relapse Visit ^b	Withdrawal Visit ^c
	Day 1 ^d	Day 2	Day 3	Day 5	day 8	Day 11	Day 15	Day 22	Day 29	Day 60	Day 90	Day 120	Day 150	Day 180	Relapse	Withdrawal
Window				+1d	-/+1d	-/+1d	-/+2d	-/+3d	-/+3d	-/+7d	-/+7d	-/+10d	-/+10d	-14/+21d		
Informed Consent Process	X															
Demographic Information	X															
Initial History Only ^e	X															
Physician Assess. Malaria Signs & Symptoms	X															
Inclusion/Exclusion Criteria	X															
Efficacy Assessments																
Parasitological Assessment (blood smear)	X ^f	X ^f	X ^f		X		X	X	X	X	X	X	X	X	X	X
Plasmodium PCR Genotyping	X														X	
Plasmodium whole genome sequencing	X														X	
Safety Assessments																
Review Concomitant Medications	X	X	X	X	X	X	X	X	X	X	X	X	X	X	X	X
Vital Signs ^g	X	X	X		X	X	X	X	X	X	X	X	X	X	X	X
Physical Examination	X	X	X		X		X	X	X	X	X	X	X	X	X	X

Protocol Activity	Visit Day															
	Screening/Treatment Period ^a							Follow-Up Period							Relapse Visit ^b	Withdrawal Visit ^c
	Day 1 ^d	Day 2	Day 3	Day 5	Day 8	Day 11	Day 15	Day 22	Day 29	Day 60	Day 90	Day 120	Day 150	Day 180	Relapse	Withdrawal
Window				+1d	-/+1d	-/+1d	-/+2d	-/+3d	-/+3d	-/+7d	-/+7d	-/+10d	-/+10d	-14/+21d		
ECG w/ Interpret. & Report ^h	X	X							X						X	X
Adverse Events Assessment ⁱ	X	X	X	X	X	X	X	X	X	X	X	X	X	X	X	X
Serious Adverse Events ^j	X	X	X	X	X	X	X	X	X	X	X	X	X	X	X	X
G6PD (phenotyping) ^k	X									X		X				
G6PD and CYP2D6 (genotyping)		X														
Ophthalmological Exam (qualified sites only)	X								X		X			X ^l		X
Laboratory Assessments																
Hematology ^m	X		X ⁿ	X	X	X	X	X	X	X	X	X	X		X	X
Clinical Chemistry ^o	X		X ⁿ	X	X	X	X	X	X	X	X	X		X	X	
Methemoglobin	X	X	X	X	X	X	X	X	X	X		X		X	X	
Urinalysis ^p	X		X	X	X	X	X	X	X	X	X	X		X	X	
Blood Draw for PGx		X ^q														
Pregnancy Test ^r	X						X		X	X				X	X	X
Health Outcomes																
Health Outcomes Assessments ^s	X						X	X ^t	X ^t	X ^t	X ^t	X ^t	X ^t	X ^t	X ^t	X ^t
Pharmacokinetic Assessments																
PK/PD Sampling ^u		X	X		X		X		X	X					X	

Protocol Activity	Visit Day															
	Screening/Treatment Period ^a							Follow-Up Period							Relapse Visit ^b	Withdrawal Visit ^c
	Day 1 ^d	Day 2	Day 3	Day 5	Day 8	Day 11	Day 15	Day 22	Day 29	Day 60	Day 90	Day 120	Day 150	Day 180	Relapse	Withdrawal
Window				+1d	-/+1d	-/+1d	-/+2d	-/+3d	-/+3d	-/+7d	-/+7d	-/+10d	-/+10d	-14/+21d		
Investigational Product																
Dispense Open Label Chloroquine	X	X	X													
Dispense Blinded Study Medication	X ^v	X ^v														
Treatment Compliance Int. - Invest.	X	X	X	X	X	X	X									
IVRS Registration	X															

a All subjects must remain hospitalized for Days 1 through 3.

b Subjects who relapse will continue to be monitored for safety and efficacy at all scheduled visits through day 180. Relapse is defined by a positive blood smear with or without vivax symptoms.

c If subjects withdraw from blinded study medication, all scheduled follow-up visits should be performed to conduct safety assessments up to and including Day 180.

d Visit Day 1 includes all screening procedures and the first day of treatment with study medication.

e Includes medical, disease and therapy histories.

f Blood smears are to be taken twice a day, 6-12 hours apart for the first 3 days, or until 2 consecutive negative thick blood smears are obtained.

g Vital signs include height and weight (screening only), blood pressure, temperature, heart rate and respiratory rate. Vital signs are to be performed twice a day on Days 1 through 3, at least 4 hours apart, and immediately prior to PK measurements.

h ECGs are to be performed at screening (in triplicate), 12 hours after the first dose of blinded study medication, and on Day 29.

i Adverse events are recorded from the time of the first dose of study medication.

j Serious adverse events are recorded from the time of consent in order to fulfil international regulatory requirements.

k G6PD phenotyping to be performed by both quantitative spectrophotometric analysis and rapid point of care test.

l Only if Day 90 ophthalmological exam shows abnormalities.

m Hematology includes hemoglobin, hematocrit, red blood cell/white blood cell/platelet counts, mean cell volume, white blood cell differential and reticulocyte count.

n Hematology and clinical chemistry on Day 3 must be reviewed prior to discharge from the hospital.

o Clinical Chemistry includes CPK, BUN, serum creatinine, total and indirect bilirubin and liver clinical chemistry.

p Mid-stream urine will be analyzed for protein, glucose, ketones, bilirubin, blood, nitrates, urobilinogen and leukocyte esterase by dipstick method.

q The pharmacogenetics sample must be collected at the earliest opportunity after randomization and during the in-clinic treatment visit (Days 1-3).

Protocol Activity	Visit Day															
	Screening/Treatment Period ^a							Follow-Up Period							Relapse Visit ^b	Withdrawal Visit ^c
	Day 1 ^d	Day 2	Day 3	Day 5	Day 8	Day 11	Day 15	Day 22	Day 29	Day 60	Day 90	Day 120	Day 150	Day 180	Relapse	Withdrawal
Window				+1d	-/+1d	-/+1d	-/+2d	-/+3d	-/+3d	-/+7d	-/+7d	-/+10d	-/+10d	-14/+21d		

- r Serum or urine pregnancy test that is routinely used at site with a test sensitivity for hCG level ≤ 25 mIU/mL. FSH serum test only for post-menopausal females with less than 6 months spontaneous amenorrhea.
- s Refer to Section 6.5 of the protocol for details on health outcome data collection.
- t Health outcomes assessments will only be collected at these visits from subjects with confirmed parasitemia or from subjects with clinically relevant hemolysis.
- u Day 2 and Day 3 PK samples must be taken 6-12 hours and 24-48 hours post TQ dose. ECGs should be taken within 10 minutes prior to the Day 2 and Day 3 PK sampling.
- v Treatment with blinded study medication will begin on either Day 1 or Day 2.

